9.6. Vital Signs, Physical Findings, and Other Observations Related to Safety

9.6.1. Vital Signs

Vital signs will include blood pressure, pulse rate, respiratory rate, and temperature.

Height will only be measured at the Screening Visit for CP543.3001 and CP543.3002. Weight and vital signs will be measured according to the Schedule of Assessments (Appendix 14.1) during each physical examination. Weight and height will be used to calculate the subject's baseline BMI.

The mean and mean change from baseline to each scheduled assessment will be summarized descriptively by treatment group and overall for each vital sign variable specified in the protocol. Change from baseline will be summarized separately for the "pre-zero" baseline and the CP543.5002 study baseline (see Section 6.2).

A listing of vital signs by subject will also be provided.

Vital signs (systolic blood pressure, diastolic blood pressure, and weight) will be assigned the grades (severities) based on CTCAE criteria. Values will be graded using CTCAE version 5.0, for those values and directions included. For systolic blood pressure and diastolic blood pressure, shift tables using CTCAE grades to compare baseline to the worst post-baseline CTCAE grade by vital sign parameters and treatment group will be produced for applicable parameters, separately for each baseline type. For weight, the frequency of worst CTCAE grades will be produced, separately for each baseline type. Values will only be included if the subject had both a baseline and post-baseline value for that parameter.

Sun Pharmaceutical Industries, Inc.
Statistical Analysis Plan – CP543.5002

Clinically notable vital signs will be identified based on the criteria below for heart rate. The number and percentage of subjects with at least 1 treatment-emergent notable value will be tabulated by treatment group, using the worst post-baseline value in either direction.

Vital Sign Parameter	Value
Heart rate	>100 bpm with increase from baseline* of ≥ 20 bpm <60 bpm with decrease from baseline* of ≥ 15 bpm

bpm = beats per minute

*CP543.5002 study baseline

The mean and standard error for weight may be summarized graphically, visit and treatment group.

9.6.2. Physical Examinations

A complete physical examination will consist of vital signs, weight, an examination of all major organ systems, with an emphasis on assessing for active signs and symptoms of infection, exposure to tuberculosis, and skin examinations for non-melanoma skin cancers. Evaluation for progressive multifocal leukoencephalopathy (PML) symptoms such as facial droop, general weakness, clumsiness, trouble speaking, personality changes, memory problems, and vision changes will be assessed.

Brief physical examinations will focus on an evaluation of safety and include vital signs, weight, abdominal palpation, and head, eyes, ears, nose and throat assessment, assessing for active signs and symptoms of infection, exposure to tuberculosis (TB), inquiry on changes to skin lesions and/or moles indicative of skin cancers, and an evaluation for PML as noted above. Physical examinations will be performed according the Schedule of Events (Appendix 14.1). A listing of the date and type of physical examinations performed will be provided. Deteriorations from baseline on physical examination should be reported as AEs and summarized as such.

9.6.3. Other Safety Measures

9.6.3.1. 12-Lead Electrocardiogram

Twelve-lead ECGs will be performed at Week 52, Week 108 (for responders only), and/or the Early Termination Visit. Individual parameters including heart rate, PR, QT, QTcF (Frederica's correction), QRS, RR intervals will be collected. If a subject is unable to attend an in-person clinic visit due to COVID-19, a 12-lead ECG may not be performed. Missed assessments will be recorded in the eCRF as due to COVID-19.

The mean and mean change from baseline to each scheduled assessment will be summarized descriptively by treatment group and overall for each 12-lead ECG variable specified in the protocol. Change from baseline will be summarized separately for the “pre-zero” baseline and the CP543.5002 study baseline (see Section 6.2); only subjects who have both a baseline and at least 1 post-baseline assessment will be included. Clinically significant ECG results will be identified based on the criteria in Table 5, and will be summarized descriptively by treatment group and overall, separately for each baseline definition. Clinically significant ECG results will

Sun Pharmaceutical Industries, Inc.
Statistical Analysis Plan – CP543.5002

be identified based on the criteria below. For each ECG parameter, the number and percentage of subjects with at least 1 treatment-emergent notable value will be tabulated overall, using the worst post-baseline value. The number and percentage will be summarized separately for the “pre-zero” baseline and the CP543.5002 study baseline (see Section 6.2). To be defined as treatment-emergent, the criteria should be met after first dose of study drug (as applicable to each baseline definition) and not met at baseline. Clinically significant ECG results for subjects who meet the criteria after first dose of study drug and are missing their baseline value will conservatively be counted as treatment-emergent.

Table 5: Clinically Significant ECG Criteria

ECG Parameter	Criteria
QTcF	Post-baseline >450 msec Post-baseline >480 msec Post-baseline \geq 500 msec Post-baseline >450 msec and \leq 480 msec Post-baseline >480 msec and \leq 500 msec Post-baseline increase >30 msec Post-baseline increase >60 msec Post-baseline increase >30 msec resulting in a post-baseline >450 msec Post-baseline increase >30 msec resulting in a post-baseline >480 msec Post-baseline increase >30 msec resulting in a post-baseline \geq 500 msec
QRS	Post-baseline \geq 120 msec and \geq 20% increase from baseline
PR	Post-baseline \geq 220 msec and \geq 20% increase from baseline
Heart rate	Post-baseline \leq 50 bpm and \geq 20% decrease from baseline

bpm = beats per minute; ECG = electrocardiogram; msec = millisecond; QTcF = QT corrected for heart rate using Fridericia’s method

A listing of electrocardiogram results will be provided. A listing of abnormal ECG findings will also be provided.

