## 1. SYNOPSIS

|   |                                |
|---|--------------------------------|
| Name of Sponsor/Company:
Sun Pharmaceutical Industries, Inc.  |                                |
| Name of Investigational Product:
CTP-543  |                                |
| Name of Active Ingredient:
deuruxolitinib   |                                |
| Title of Study:
A Multicenter, Open-label, Extension Study to Assess the Long-Term Safety and Efficacy of CTP-543 in Adult Patients with Moderate to Severe Alopecia Areata   |                                |
| Study Number: CP543.5002   |                                |
| Study center(s): Multicenter; European Union   |                                |
| Studied period (years):
Estimated date first patient enrolled: September 2021
Estimated date last patient completed: July 2024   | Phase of development: 3 |
| Objectives:
The overall objectives of the study are to evaluate long-term safety of CTP-543 and to assess long-term effects of CTP-543 on treating hair loss in adult patients with moderate to severe alopecia areata.   |                                |
| Methodology:
Patients with alopecia areata who previously participated in a qualifying Phase 3 clinical trial (study CP543.3001 or study CP543.3002) with CTP-543 and who complete the 24-week Treatment Period on Study Medication (active or placebo), have the opportunity to enroll in this open-label extension (OLE) study in which they will receive daily treatment with CTP-543. At the Week 52 visit, patients will be assessed for treatment success (Responders) defined as patients having an absolute SALT score of $\leq 20$ at Week 52. These Responders will be eligible to continue in the OLE extension for up to a maximum of one additional year. Non-responders will complete the study at Week 52.
Safety will be evaluated by clinical laboratory measurements, AEs and physical exams. SARS-CoV-2 testing will be performed at all visits. SALT assessments will be performed periodically for efficacy, as described in the Schedule of Events Tables (Table 1 and Table 2). |                                |

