4.1. Treatment Group Presentation by Analysis

For analyses of disposition, demographics, baseline characteristics, concomitant medications, and medical history, subjects will be analyzed under their first actual treatment received (8 mg BID or 12 mg BID) in CP543.5002. The following treatment columns will be used:

- CTP-543 8 mg BID
- CTP-543 12 mg BID
- Total CTP-543

Summary tables for the laboratory evaluations, vital signs, and ECGs will include the following treatment columns referring to the starting dose in CP543.5002 and modified dose, if applicable (CP543.5002 initial treatment to CP543.5002 modified treatment):

- CTP-543 8 mg BID
- CTP-543 12 mg BID
- CTP-543 8 mg BID to CTP-543 12 mg BID
- CTP-543 12 mg BID to CTP-543 8 mg BID
- Total CTP-543

For analyses of laboratory evaluations, vital signs, and ECGs, the treatment groups CTP-543 8 mg BID and CTP-543 12 mg BID refer to subjects who initially received CTP-543 8 mg BID or CTP-543 12 mg BID, respectively, during CP543.5002 and received no qualifying dose changes. For clarity, for purposes of identifying treatment groups for these analyses, the initial dose will be the first dose that was dispensed for at least 2 visits; if no dose meets that criteria, then the initial dose is the first dose actually received in CP543.5002. A qualifying dose change is any dose change from the initial dose that spans more than one planned visit in CP543.5002 (i.e., the altered dose was dispensed at two or more consecutive visits). The treatment group CTP-543 8 mg BID to CTP-543 12 mg BID refers to subjects who received a qualifying dose change from 8 mg BID to 12 mg BID during CP543.5002. In the event of more than one qualifying dose change, only the first qualifying dose change will be considered. The treatment group CTP-543 12 mg BID to CTP-543 8 mg BID is defined similarly for qualifying dose changes from 12 mg BID to 8 mg BID.

If there are no subjects with dose adjustments meeting the criteria defined above, the CTP-543 8 mg BID to CTP-543 12 mg BID and CTP-543 12 mg BID to CTP-543 8 mg BID columns may be excluded from summaries which utilize the Safety population.

For analyses of efficacy, subjects will be classified in the same treatment groups as above for laboratory evaluations, vital signs and ECGs:

- CTP-543 8 mg BID

Sun Pharmaceutical Industries, Inc.
Statistical Analysis Plan – CP543.5002

- CTP-543 12 mg BID
- CTP-543 8 mg BID to CTP-543 12 mg BID
- CTP-543 12 mg BID to CTP-543 8 mg BID

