8.2.3.1. Analysis of the Efficacy Endpoint Post-Dose Reduction

[REDACTED]

Subjects with loss of response will be defined as having an absolute SALT score > 50 ; subjects with no loss of response will be defined as having an absolute SALT score ≤ 50 . Responders at pre-dose reduction baseline will be defined as having an absolute SALT score ≤ 20 at pre-dose reduction baseline; non-responders will be defined as having an absolute SALT score > 20 . A line graph of the absolute change from pre-dose reduction baseline SALT score vs. visits since dose reduction will also be produced for subjects who had a dose reduction from CTP-543 12 mg to 8 mg on or after 28 Apr 2023 due to the urgent safety measures.

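### Whole-study worst-value ECG and vital-sign tables mix 1 ECG and 8 visits with 2 and 15, so the unchanged 12 mg column is generally understated and the 12-to-8 mg column overstated

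*SAP*

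**What the plan says.** **Counting rule.** SAP 9.6.3.1 flags ECG results against Table 5 and states that "the number and percentage of subjects with at least 1 treatment-emergent notable value will be tabulated overall, using the worst post-baseline value". Just before that, it says that clinically significant results "will be summarized descriptively by treatment group and overall, separately for each baseline definition". SAP 9.6.1 counts notable heart rates by treatment group, "using the worst post-baseline value in either direction". For blood pressure it plans "shift tables using CTCAE grades to compare baseline to the worst post-baseline CTCAE grade by vital sign parameters and treatment group", and for weight the frequency of worst grades. No cut-off date or exposure adjustment is attached to any of these tables.

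**Observation.** "Twelve-lead ECGs will be performed at Week 52, Week 108 (for responders only), and/or the Early Termination Visit". Vital signs are taken at every physical examination, so at every clinic visit after baseline. Non-responders finish at Week 52; responders may go on to Week 108.

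**Columns.** Under SAP 4.1 the 8 mg and 12 mg columns for vital signs and ECGs hold only subjects who "received no qualifying dose changes". A change qualifies when the altered dose is dispensed at two or more consecutive visits; those subjects move to a 12-to-8 or 8-to-12 column. After the urgent safety measure, everyone on 12 mg who stays in the trial goes to 8 mg. SAP 8.2.3.1 dates this by referring to a "dose reduction from CTP-543 12 mg to 8 mg on or after 28 Apr 2023". The Protocol Synopsis gives "Estimated date first patient enrolled: September 2021".

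**Contrast.** SAP 9.5 shows potentially clinically significant laboratory values by post-baseline visit as well as overall. SAP 9.6 does not do this for the tables discussed here.

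**The concern.** The chance of at least one abnormal value grows with the number of looks, and so does the worst grade. Here the number of looks depends on Week 52 response and, through the SAP 4.1 columns, on whether a 12 mg patient continued after the dose was withdrawn. Two columns with identical risk per assessment can then show clearly different percentages. Long-term safety is a stated objective and one dose was stopped for safety, so readers will compare these columns. They could take the unchanged 12 mg column as reassuring, or take the 12-to-8 column as showing harm in patients who stepped down, when the difference is only the amount of observation.

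**Working it through.** The plan states no event rate for these tables, so there is no figure to reproduce.

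**1. Scheduled looks (schedule of events).** Visits after baseline: Weeks 4, 8, 12, 20, 28, 36, 44, 52 = 8. Responders add Weeks 60, 68, 76, 84, 92, 100, 108 = 7, in total 15. ECGs: Week 52 = 1; Weeks 52 and 108 = 2. Ratios for completers: 15/8 = 1.875 and 2/1 = 2.

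**2. Can the unchanged 12 mg column hold a Week 108 ECG?** With enrolment on 1 September 2021 as Day 1, 28 April 2023 is Day 605. Week 108 is targeted at Day 757 and its ±3-day window opens on Day 754. On Day 605 the patient is between Week 84 (Day 589) and Week 92 (Day 645). A patient who stays gets 8 mg at Weeks 92 and 100, which is a qualifying change, and so is in the 12-to-8 column by Week 108. Later entrants are further from Week 108. A Week 108 ECG can therefore fall under 8 mg or 12-to-8, but not under unchanged 12 mg.

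**3. Percentages at equal risk.** P(at least one) = 1 − (1 − p)^k, with p = 5% assumed:
- 1 ECG: 5.0%; 2 ECGs: 1 − 0.95² = 9.75%
- 8 visits: 1 − 0.95⁸ = 33.7%; 15 visits: 1 − 0.95¹⁵ = 53.7%

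Take the CP543.3002 Week 24 response rates (Protocol 4.2: 33.0% on 8 mg, 38.3% on 12 mg) as a stand-in for Week 52, with no dropout and everyone continuing:
- 8 mg, ECG: 0.67 × 5.0 + 0.33 × 9.75 = 6.6%
- 8 mg, vital signs: 0.67 × 33.66 + 0.33 × 53.67 = 40.3%
- 12 mg unchanged (non-responders only): 5.0% and 33.7%
- 12-to-8 (responders only): 9.75% and 53.7%
- All 12 mg starters, ECG: 0.617 × 5.0 + 0.383 × 9.75 = 6.8%
- All 12 mg starters, vital signs: 0.617 × 33.66 + 0.383 × 53.67 = 41.3%

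**4. With dropout and refusal.** These rows come from a simulation with p = 5%, independence, uniform entry from mid-September 2021 to early July 2022, 15% annual dropout, and a varying share of 12 mg patients continuing on 8 mg. Cells show ECG % / vital signs %.

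| Response (8, 12 mg); share continuing | 8 mg | 12 mg | 12-to-8 | All 12 mg starters |
|---|---|---|---|---|
| 33.0, 38.3%; 90% | 6.3 / 37.2 | 5.3 / 31.7 | 9.75 / 53.2 | 6.5 / 37.5 |
| 45, 45%; 60% | 6.8 / 39.1 | 5.8 / 32.7 | 9.75 / 53.2 | 6.6 / 37.1 |
| 33.0, 38.3%; 0% | 6.3 / 37.2 | 6.2 / 33.7 | none | 6.2 / 33.7 |
| 29.6, 41.5%; 0% | 6.2 / 36.7 | 6.3 / 33.9 | none | 6.3 / 33.9 |

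The unchanged 12 mg column lay below 8 mg in every scenario run except the ECG figure in the last row.

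**5. Within-patient correlation.** Replacing independence in step 3 by a beta-binomial with an assumed intraclass correlation of 0.3 gives ECG 5.0% (12 mg), 6.1% (8 mg), 8.3% (12-to-8), and vital signs 17.9%, 19.6%, 22.9%. At 0.5 the figures are 5.0%, 5.8%, 7.4% and 12.9%, 13.7%, 15.5%. The order stays and the gaps narrow.

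**The case against.** **A stronger reading to resist.** A reader might infer that the percentages follow response and so make 12 mg look safer. The documents do not support this. Protocol 4.2 reports higher Week 24 response on 12 mg in both trials (41.5% against 29.6%; 38.3% against 33.0%), so response alone pushes 12 mg up slightly: with the CP543.3001 rates, no dropout and p = 5%, ECG is 0.585 × 5.0 + 0.415 × 9.75 = 7.0% on 12 mg against 0.704 × 5.0 + 0.296 × 9.75 = 6.4% on 8 mg. The low 12 mg column arises because SAP 4.1 moves its continuing responders elsewhere. Pooling all 12 mg starters reverses or nearly removes the gap in most scenarios; it stays visible for vital signs when many leave at the switch.

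**12 mg patients can have looks after Week 52.** A responder who declines 8 mg at Day 605 has had 12 visits and then an Early Termination Visit with a second ECG. This stands and raises the 12 mg column, as the rows with 0% continuing show.

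**Repeated measures are correlated.** This also stands. Independence is the favourable case for the concern; step 5 shows how far the gaps shrink.

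**Ambiguous dose display.** The quoted ECG sentence says only that counts are tabulated overall. If that means the Total column alone, that table has no dose contrast. The sentence on clinically significant ECG results before it specifies treatment groups, and the vital-sign tables are by treatment group, so the point survives, but the wording needs clarifying.

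**Descriptive analysis with other displays.** Nothing is tested, and mean changes by visit, exposure summaries and listings let a reader see that follow-up differs. None gives the proportion of subjects with an abnormal value over a common period.

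**Conclusion.** The point holds in limited form. The notable heart-rate, worst-grade blood-pressure and weight, and Table 5 ECG tables compare subjects over unequal observation set by Week 52 response. At equal risk per assessment, the unchanged 12 mg column is generally understated and the 12-to-8 column overstated. In the illustration, ECG is 5.0%, 6.6% and 9.75% and vital signs 33.7%, 40.3% and 53.7% for 12 mg, 8 mg and 12-to-8.

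The scheduled counts and the dating argument come from the documents, given the estimated September 2021 start. The sizes rest on assumptions the documents do not settle: risk per assessment, independence, Week 52 response, dropout and the share continuing on 8 mg. Dose changes at the investigator's discretion (SAP 7.2) are left out. The figures use the CP543.5002 baseline; under the pre-zero baseline, a carried-over qualifying-trial ECG may add one look for previously active patients. This should be corrected before database lock, but it is not evidence that the plan favours the 12 mg starting dose.

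**What to change.** For the CP543.5002-baseline versions of these tables in SAP 9.6.1 and 9.6.3.1, add:

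- **(a)** counts from first OLE dose through Week 52, by starting OLE dose (8 mg, 12 mg), censored at the first qualifying dose change or with later values shown separately. This is the table to read across doses. Starting dose is needed because the SAP 4.1 columns stay selected on response and continuation even with a Week 52 cut.
- **(b)** counts after Week 52 through Week 108, for continuing responders only.

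In both, use subjects assessed in the period as the denominator and print it, since the SAP default is the header N. Give results by visit as SAP 9.5 does for laboratory values, and state whether the Table 5 counts appear by treatment group. Keep the whole-study columns and the pre-zero tables, with a footnote that observation time differs by response and that the 12-to-8 column is selected on continuation.

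With (a), every completer followed to Week 52 without censoring contributes 1 ECG and 8 visits, so at an equal 5% risk both doses show 5.0% and 33.7%. Dropout before Week 52 remains and would show in the denominators. Some late entrants switch before Week 52: counting 108 weeks (756 days) back from 31 July 2024 gives entry on 6 July 2022, which is Day 297 on 28 April 2023. The SAP should say how their values after the switch are shown.

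Cost: SAP wording and one extra set of tables from data already collected, with small counts in (b).

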9. SAFETY EVALUATION

9.1. Overview of Safety Analysis Methods

All safety summaries will be descriptive with no statistical hypothesis testing and based on the Safety Population. Safety assessments will be summarized by treatment group and overall, as specified in Section 4. All safety endpoints will be listed in by-subject data listings.

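### In the two bounded QTcF rows of SAP Table 5, a fall from a higher baseline counts as treatment-emergent, and a value of exactly 500 msec also meets the top row

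*SAP*

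**What the plan says.** SAP Section 9.6.3.1 (12-Lead Electrocardiogram) asks for counts of subjects with clinically significant ECG results, judged by the criteria in SAP Table 5. The counts are made once against the pre-zero baseline and once against the CP543.5002 study baseline. A result is treatment-emergent when "the criteria should be met after first dose of study drug (as applicable to each baseline definition) and not met at baseline". For each ECG parameter, the count is of subjects with "at least 1 treatment-emergent notable value will be tabulated overall, using the worst post-baseline value". A subject who meets a criterion after dosing and has no baseline value is counted as treatment-emergent.

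Table 5 has ten QTcF rows of three kinds:

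- three open-ended rows: above 450, above 480, and "Post-baseline \geq 500 msec";
- two bounded rows: "Post-baseline >450 msec and \leq 480 msec" and "Post-baseline >480 msec and \leq 500 msec";
- five rows that require a rise of more than 30 or more than 60 msec, three of them combined with a threshold.

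The SAP gives this schedule: "Twelve-lead ECGs will be performed at Week 52, Week 108 (for responders only), and/or the Early Termination Visit".

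**The concern.** A treatment-emergent row should hold subjects who got worse on treatment. The SAP's test is only whether the same criterion was met at baseline. In a band with an upper limit, a subject can fail the criterion at baseline by being too high as well as by being low enough. A subject whose QTcF shortens into the band then appears as a new abnormality, and the row reports an improvement as a safety finding.

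Elsewhere in the same table direction is built in. The QRS row, for instance, reads "Post-baseline \geq 120 msec and \geq 20% increase from baseline". The PR row also needs an increase and the heart rate row a decrease. The two bounded QTcF rows have no such condition.

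The second matter is the boundary at 500 msec. The upper band includes 500, and so does the top row. The two bands and the top row therefore do not split the values above 450 cleanly.

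**Working it through.** **Inputs.** The rule and the ten QTcF criteria come from SAP Section 9.6.3.1 and Table 5. I take worst to mean longest QTcF. Write *b* for baseline and *w* for the worst post-baseline value, both in msec. A row is flagged when *w* meets its criterion and *b* does not. The plan states no figure to reproduce.

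**Step 1: open-ended rows.** For the row above *c*, a flag needs *w* > *c* and *b* ≤ *c*, so *w* > *b*. For 500 or more, it needs *w* ≥ 500 and *b* < 500, so again *w* > *b*. These rows never flag a fall.

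**Step 2: increase rows.** A flag needs *w* − *b* > 30 or > 60. These rows never flag a fall.

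**Step 3: bounded rows.** For the band above *L* up to *U*, not met at baseline means *b* ≤ *L* or *b* > *U*.

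- If *b* ≤ *L*, then *w* > *L* ≥ *b*, a true rise.
- If *b* > *U*, then *w* ≤ *U* < *b*, always a fall, and it is flagged.

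**Step 4: worked cases, rule applied row by row.**

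| Baseline | Worst later value | Change | Flagged in a bounded row? |
|---|---|---|---|
| 490 | 470 | −20 | Yes, lower band |
| 510 | 490 | −20 | Yes, upper band |
| 510 | 470 | −40 | Yes, lower band |
| 481 | 480 | −1 | Yes, lower band |
| 470 | 490 | +20 | Yes, upper band (correct) |
| 440 | 470 | +30 | Yes, lower band (correct) |

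The four falls are flagged in no other QTcF row.

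**Step 5: enumeration.** Take all integer pairs from 380 to 560 with *w* < *b*. The lower band flags 30 values of *w* × 80 baselines (481 to 560) = 2,400 pairs. The upper band flags 20 values of *w* × 60 baselines (501 to 560) = 1,200. The total is 3,600, and the other eight rows contribute none. The total depends on the range chosen. It confirms which rows are affected and says nothing about how many subjects are.

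**Step 6: the value 500.** Among the two bands and the top row, 499 meets only the upper band, 501 only the top row, and 500 meets both. So 440 to 500 is treatment-emergent in both, and 501 to 500 is a new upper-band result after a 1 msec fall.

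**Step 7: after the fix.** Requiring *b* ≤ *L* removes exactly the second case in Step 3 and nothing else. The 3,600 flagged falls become 0. The rises 440 to 470 and 470 to 490 are still flagged, and 500 falls only in the top row of the three.

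**The case against.** **The damage is contained.** This stands. Eight of the ten QTcF rows never flag a fall. For 490 to 470 the emergent rows above 450 and above 480 and all the increase rows stay empty, so a careful reader could spot the odd entry. The SAP also summarises mean change and lists ECG results and abnormal findings. Moreover, "All safety summaries will be descriptive with no statistical hypothesis testing and based on the Safety Population" (SAP Section 9.1), and no decision rule depends on these rows.

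**The text can be read differently.** The count is framed per ECG parameter, so one could require that no QTcF criterion at all is met at baseline. Then 490 to 470 is not flagged, but neither is a real worsening from 470 to 490. The SAP does not state that reading, and applying the rule row by row is more natural.

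**Taking the worst value protects against it.** Only in part. If any later value is at or above baseline, the false flag does not arise. If even the worst value lies in a lower band, it does. A non-responder normally has one scheduled post-baseline ECG in this study, so there is often little to choose from.

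**Two stronger readings are tempting and not supported.** A reader might infer that a particular number of subjects will be miscounted. The documents give no QTcF distribution, the Protocol sets no sample size (Number of patients, Synopsis), and the qualifying trials' entry criteria are not available here. Protocol Sections 7.1 and 7.2 contain no QTcF limit, so a high baseline is not specifically excluded, but that does not show that one occurs. A reader might also infer that the QTcF categories overlap by mistake throughout. The open-ended rows are nested by design and contain the bands. The inconsistency is a single boundary, and the top row is an open-ended threshold, not a second bounded band.

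**Conclusion.** The point holds as a minor correction. As written, the two bounded QTcF rows count any subject whose baseline is above the band and whose worst later value is inside it, and every such subject has improved. This follows from the rule itself, given the row-by-row reading and worst meaning longest. The overlap at 500 is also real and affects only a value of exactly 500 msec.

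The number of subjects affected is unknown and may be zero. It is limited to subjects with a baseline above 480 msec whose worst later value falls into a lower bounded band, plus any value of exactly 500. Those who fall to 450 or below, stay in the same band or rise are not miscounted by the rule. The effect is on descriptive safety counts only. It is still worth correcting, because long-term safety is a study objective and a row labelled treatment-emergent should not contain improvements.

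**What to change.** In SAP Section 9.6.3.1 and Table 5:

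1. For the two bounded QTcF rows, count a result as treatment-emergent only if the worst post-baseline value is in the band and the baseline is at or below the band's lower limit (450 or 480 msec).
2. State that the existing rule for a missing baseline is kept. Without that sentence, the new condition could be read as excluding those subjects, since a missing value cannot be at or below a limit.
3. Change the upper band to above 480 and below 500 msec.
4. Apply all of this to both the pre-zero and the CP543.5002 study baseline.

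The cost is two short text edits and a matching change in the program and table shell. Because SAP text changes, Section 4.1 implies re-approval. No new data are needed, and Step 7 of the working shows that no true worsening is lost. If the SAP can no longer be amended, the same definition can be applied and described in the clinical study report as a deviation, as SAP Section 2 provides.
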